9.3.2.3 Further outcomes

The further outcomes are as follows:

- A GPPASI 75 at Week 4 (if collected)
- A GPPASI 50 at Week 1 (if collected)
- A GPPASI 50 at Week 4 (if collected)
- The percent reduction in GPPASI from baseline at Week 1 (if collected)
- The percent reduction in GPPASI from baseline at Week 4 (if collected)
- Change from baseline in pain VAS score at Week 4 (if collected)
- Change from baseline in PSS score at Week 4 (if collected)
- Investigator's overall effectiveness assessment at Week 1 and/or Week 4

The GPPASI is provided in [Annex 5](#). It is an adaptation for GPP patients of the Psoriasis Area and Severity Index (PASI), an established measure of severity and area of psoriatic lesions in patients with psoriasis [[R96-3541](#)]. Similar adaptations have been used for palmo-plantar psoriasis (PPP) [[R16-3360](#)]. In the GPPASI, the induration component was substituted with the pustules' component. It is a tool that provides a numeric scoring for a patient's overall GPP disease state, ranging from 0 to 72. It is a linear combination of percent of surface area of skin that is affected by erythema, pustules and scaling and the severity of erythema, pustules, and scaling (desquamation) over 4 body regions.

The pain VAS instrument is provided in [Annex 6](#). The pain VAS is a unidimensional measure of pain intensity [[R18-1989](#)]. The respondent is asked to place a vertical (|) mark on the horizontal line to indicate the severity of the pain. Using a ruler, the score is determined by measuring the distance (mm) on the 10-cm line between the "no pain" anchor and the

patient's mark, providing a range of scores from 0–100. A higher score indicates greater pain intensity.

The PSS instrument is provided in [Annex 7](#). The PSS is a 4-item patient-reported outcome (PRO) instrument that was developed to assess the severity of psoriasis symptoms in patients with moderate to severe psoriasis [[R18-1990](#)]. The symptoms included are pain, redness, itching, and burning. Current symptom severity is assessed using a 5-point scale ranging from 0 (none) to 4 (very severe). The symptom scores are added to an unweighted total score (range: 0 to 16).

The overall effectiveness assessment is performed at the investigator's discretion. The information includes:

- Improved: If determined as there is any effect of maintaining or improving symptoms.
- Unchanged: If symptoms have not been changed compared with before administration, and not determined as there is any effect of maintaining symptoms.
- Aggravated: If symptoms are worse than before administration.
- Unassessable: If it cannot be determined.

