9.7.1.3 Number of cases to effectiveness assessment

These cases include those who signed the data release consent form to participate in this study, visited as per the study schedule, took Spesolimab IV, and were evaluated for the effectiveness.

Based on the MFDS guideline, the cases below shall be excluded from effectiveness analysis (defined below):

- a. Patients excluded from the safety analysis set listed in section [9.7.1.3](#).
- b. Patients missing information of effectiveness assessment listed in section [9.3.2.2](#).

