9.7.3 Effectiveness analysis

Effectiveness analysis will be performed on the effectiveness set.

Effectiveness analyses will be performed by subgroup based on demographics and baseline characteristics.

The standard descriptive statistical parameters (number of patients, mean, standard deviation, median, minimum, maximum, etc.) will be summarized.

The changes of the effectiveness outcomes from baseline will be compared in an exploratory sense via paired t-test.

For investigator's overall effectiveness evaluation, the number and percentage of patients will be presented. If the result of overall evaluation is 'improved', it will be classified as 'effective'. If the result of overall evaluation is 'unchanged' or 'aggravated', it will be classified as 'ineffective'.

'Effective' and 'ineffective' will be reported using numbers of patients, percentages with 95% CIs.

Categorical variable will be reported using numbers of patients, numbers of patients assessed as 'effective', effective rates and 95% CIs. Effectiveness will be analyzed by Pearson's chi-square test or Fisher's exact test to determine if there are statistically significant differences.

Continuous variable will be reported using numbers of patients. Odds ratio and 95% CIs by simple logistic regression will be summarized.

To estimate any factors that are thought to influence an effective rate, logistic regression analysis and/or poisson regression will be conducted, and for statistically significant covariates the meaning will be described.

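### The investigator's 'effective' rate can count a patient who is no better than before dosing, because 'Improved' includes a judged maintaining effect

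*Protocol*

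**What the plan says.** Section 9.3.2.3 lists the investigator's overall effectiveness assessment, at Week 1 and/or Week 4, among the further outcomes and leaves it to the investigator's discretion. Of its four categories, three matter here:

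- The top category is worded "Improved: If determined as there is any effect of maintaining or improving symptoms".
- The one below it carries a double condition and is worded "Unchanged: If symptoms have not been changed compared with before administration, and not determined as there is any effect of maintaining symptoms".
- A residual category is worded "Unassessable: If it cannot be determined".

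The fourth, 'Aggravated', covers symptoms worse than before administration.

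Section 9.7.3 reduces these to two classes. The success class is set by "If the result of overall evaluation is 'improved', it will be classified as 'effective". The failure class takes two of the remaining ratings, through "If the result of overall evaluation is 'unchanged' or 'aggravated', it will be classified as 'ineffective". For reporting, the same section adds: "Effective' and 'ineffective' will be reported using numbers of patients, percentages with 95% CIs". The chi-square or Fisher comparisons use the effective rate, as does the search by logistic and/or Poisson regression for factors that influence it.

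Section 9.2.2.2 requires a GPP flare at entry, section 9.1 describes a single-arm study, and section 9.5 sets the target at 21 patients. Section 9.7.1.3 excludes from the effectiveness set a group described as "Patients missing information of effectiveness assessment listed in section"; the reference there is to 9.3.2.2, which lists the GPPGA outcomes and not the overall assessment.

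**The concern.** The treatment is given for an acute flare, so symptoms held at their starting level are symptoms still at flare level. A definition of success that admits a maintaining effect suits prevention of worsening better than resolution of a flare.

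Whether such a patient lands in 'effective' or 'ineffective' depends on the investigator's belief about what would have happened untreated. The protocol gives no criterion for that belief. Section 9.9.2 acknowledges that assessment criteria may differ among investigators but proposes no remedy for this category.

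The effective rate could thus overstate response and sit well above the GPPGA response rates in the same report, and the factor tests built on it would inherit the misclassification. A smaller matter is that the two-class rule covers three of the four categories, so the base of the percentage is open.

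**Working it through.** The protocol states no effective rate, power or formula-based sample size on this point, so there is no figure to reproduce. The check is a reading of the definitions, followed by an illustration.

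**Reading the definitions together.** Take a patient whose symptoms are the same as before administration.

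1. 'Aggravated' does not apply.
2. 'Unchanged' needs two things: no change, and "not determined as there is any effect of maintaining symptoms".
3. If the investigator does determine a maintaining effect, 'Unchanged' is ruled out and the definition of 'Improved' is met.
4. Section 9.7.3 then classes the patient as effective.

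The second condition in 'Unchanged' has work to do only if some patients with no change are meant to fall elsewhere. Apart from 'Unassessable', 'Improved' is the only place left for them.

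**Place of 'unassessable'.** A patient rated unassessable who has GPPGA data stays in the effectiveness set, because the exclusion refers to 9.3.2.2. Section 9.7.3 gives that patient no class. Whether the patient counts in the denominator is not stated.

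**Size.** Inputs: N = 21 (section 9.5), all assumed to reach the effectiveness set. The other counts are assumptions, since the protocol gives none: 12 patients truly improved, m = 0 to 4 maintained, u = 0 to 4 unassessable. Intervals are exact (Clopper-Pearson) 95%.

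Rate for true improvement = 12/21. Rate under the protocol's wording with everyone in the denominator = (12 + m)/21. Each maintained patient adds 1/21 = 4.8 points.

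| Maintained (m) | Rate over all 21 | 95% CI |
|---|---|---|
| 0 | 12/21 = 57.1% | 34.0 to 78.2 |
| 2 | 14/21 = 66.7% | 43.0 to 85.4 |
| 4 | 16/21 = 76.2% | 52.8 to 91.8 |

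The increases are 2/21 = 9.5 points and 4/21 = 19.0 points.

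If unassessable patients were also left out, the rate would be (12 + m)/(21 − u):

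- m = 0, u = 2: 12/19 = 63.2%; u = 4: 12/17 = 70.6%.
- m = 2, u = 2: 14/19 = 73.7% (48.8 to 90.9), of which 7.0 points come from the smaller denominator (73.7 − 66.7).
- m = 4, u = 4: 16/17 = 94.1% (71.3 to 99.9), of which 17.9 points come from the smaller denominator (94.1 − 76.2).

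These last figures need a step that the protocol does not state, so they are kept apart from the table.

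**The case against.** The case on the other side has real weight.

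- **The categories are formally exclusive.** A reader might infer that 'Improved' and 'Unchanged' overlap. They do not: a determined maintaining effect takes a patient out of 'Unchanged'. What stands is that the dividing line rests on an unanchored judgement.
- **Stability alone is not success.** The investigator must determine an effect. 'Improved', unlike 'Unchanged' and 'Aggravated', is also not tied to the state before administration, so at Week 4 maintaining could mean holding a response already gained. The text does not exclude that reading. Nor does it confine the category to it, and the wording of 'Unchanged' points the other way.
- **Not every analysis depends on this rating.** A reader might infer that all subgroup work does. Section 9.7.3 provides for effectiveness analyses by subgroup in general and for paired t-tests on changes from baseline. Only the tests and regressions framed around 'effective' are affected.
- **The denominator could be settled in the SAP.** That is right. The protocol does not say that unassessable patients are dropped. It also calls for the number and percentage of patients for the overall evaluation, which on a natural reading would show all four categories. The denominator is therefore a secondary point.
- **The outcome is exploratory and ranks below the GPPGA outcomes.** Also right. Nothing in the protocol makes this a headline rate.
- **The wording may follow a regulatory convention.** The protocol does not say so for these categories, but the fix should allow for it.

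The SAP argument does not reach the main point. Once improved and maintained patients are recorded under one option, no later analysis of that variable can tell them apart.

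**Conclusion.** The concern holds in a limited form. The protocol's definition allows a patient no better than before administration to be counted as effective on an unanchored judgement, and the effective rate and its factor tests can overstate response as a result. The direction follows from the wording; the amount does not. It is 4.8 points per maintained patient if all 21 are analysed, and zero if no patient is rated that way. The range of 66.7% to 76.2% against 57.1% rests on assumed counts.

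The missing class for 'unassessable' is a gap to close, not an error shown to bias the result. The primary safety outcomes and the secondary GPPGA responder outcomes are unaffected. This is a low-priority correction, worth making because it has to be made at data capture.

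**What to change.** **Main change.** In section 9.3.2.3 and the eCRF, make 'Improved' mean better than before administration and add 'Maintained' as a separate option. In section 9.7.3, count only 'Improved' as effective, and report the combined improved-or-maintained rate alongside in case the regulator expects the current wording. A patient holding a response already gained is better than before administration and remains 'Improved', so this also removes the Week 4 ambiguity.

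**Secondary changes.**

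- Report the number of unassessable patients explicitly. Give the effective rate over all patients in the effectiveness set, with a sensitivity analysis that excludes the unassessable.
- Run the same factor tests on the GPPGA responder outcomes of section 9.3.2.2 alongside the global rating. The scores are already mandatory, so no new data are needed.

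**Cost.** One extra eCRF option, a few lines of protocol text, and a reported effective rate that may be lower.

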9.3.3 Covariates

- 1) Patient characteristics
 - Demographics: age, gender, current pregnancy status, current breastfeeding status, smoking status, alcohol intake status
 - Physical examination: height, weight, blood pressure, body temperature, pulse rate
 - Disease information: duration of disease, IL-36RN mutation status, medical history, past / concomitant medications or therapies, history and frequency of GPP flares, comorbidities (CV, hepatic or renal impairments, infection, skin diseases (i.e., plaque psoriasis)), family history
- 2) Spesolimab IV administration status: total duration of administration, total administered dose, average daily dose
- 3) Subsequent exposure to subcutaneous Spesolimab: total duration of administration, total administered dose
- 4) Patients of special investigation: pediatric population, geriatric population, pregnant women, lactating women, hepatic impairment, renal impairment
- 5) Laboratory test results
- 6) Others

9.4 DATA SOURCES

This study will be carried out in the manner of successive observation that the investigator will be asked to put clinical data in an electronic data capture (EDC) system from the patient who was initially administered the drug following the study start date to the requested number of patients without omission.

9.5 STUDY SIZE

The enrolment target is 21 patients for a total of 6 years, considering the prevalence of generalized pustular psoriasis with acute flares in Korea and the market conditions. [REDACTED] is committed to collecting data from all patients who receive Spesolimab IV within a 2-year period after the product's launch (complete enumeration).

9.6 DATA MANAGEMENT

Patients' data will be collected by EDC system. The data management procedures to ensure the quality of the data are described in detail in the data management plan (DMP). Data management and statistics will be outsourced to a qualified CRO. DMP will be developed following Boehringer Ingelheim and/or CRO relevant SOPs.

9.7 DATA ANALYSIS

The statistical analysis plan for the study is summarized below. Full details of the statistical analysis will be documented in the Statistical Analysis Plan (SAP), which will be finalized before the end of data collection.

9.7.1 Analysis sets

The safety analysis will comprise all patients who is administered Spesolimab IV and is completed at least one time of safety follow-up.

9.7.1.1 Number of cases to CRF collection

This number means the number of patients who signed the data release consent form to participate in the study, with a record of taking Spesolimab IV once at least.

9.7.1.2 Number of cases to safety assessment

These include those who signed the data release consent form to participate in this study, took Spesolimab IV once at least, and were followed up by the investigator once or more.

Based on the MFDS guideline, the cases below shall be excluded from safety analysis (defined below):

- a. Patients who did not signed (signature missing), or patients who signed on the data release consent form prior to the contract date
- b. Patients who took Spesolimab IV prior to the contract date
- c. Patients who took Spesolimab IV prior to signing the data release consent form
- d. Patients who have not taken Spesolimab IV
- e. Patients who do not meet the inclusion/exclusion criteria
- f. Follow-up failure: Patients whose safety information cannot be obtained due to lost-to-follow-up
- g. Patients who were prescribed Spesolimab IV for indications outside the local label

However, cases enrolled during the complete enumeration period within 2 years of product launch will be included in the safety set even if the patients who took Spesolimab IV prior to the contract date or prior to signing the data release consent form.

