9.2.2.2 Inclusion criteria

- ① Patients starting Spesolimab IV for the first time in accordance with the approved label in Korea (complete enumeration for the first 2 years after product launch)
- ② Patients with GPP flare
- ③ Age \geq 19 years at enrolment
- ④ Patients who have signed the data release consent form

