9.3.2 Outcomes

9.3.2.1 Primary outcomes

The primary outcomes are the safety outcomes until study completion, calculated as the incidence of:

- Adverse events (AEs)
- Adverse drug reactions (ADRs)
- Serious adverse events (SAEs)
- Serious adverse drug reactions (SADRs)
- Unexpected adverse drug reactions
- Adverse events of special interest (AESIs)
- Adverse events leading to temporary or permanent discontinuation
- Adverse events leading to death

Assessment of safety:

- AE (event name / symptom / sign)
- Onset date and end date
- Intensity (mild / moderate / severe)
- Seriousness (serious / non-serious)
- Outcome of the event (recovered / not yet recovered / sequela / fatal / unknown)
- Causality (certain / probable-likely / possible / unlikely / conditional-unclassified / unassessable-unclassifiable)
- Action taken with study drug due to AE (dose not changed / dose reduced / dose increased / drug withdrawn / not applicable)
- AESIs (systemic hypersensitivity reactions including infusion reactions and anaphylactic reaction / severe infections / opportunistic and mycobacterium tuberculosis infections)

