11.2 ADVERSE EVENT AND SERIOUS ADVERSE EVENT COLLECTION AND REPORTING

The investigator shall maintain and keep detailed records of all AEs in their patient files.

Collection of adverse events

The study is a non-interventional study in real-world situation and will be conducted within the conditions of the approved marketing authorization. For this reason, the following AE collection and reporting requirements have been defined.

All serious adverse events, non-serious adverse events and AESIs occurring from the signing date on data release consent form to the end of the study need to be collected, documented and reported to the sponsor using the AE page of eCRF.

The investigator carefully assesses whether an AE constitutes an ADR using the information below.

Causal relationship of adverse event

The definition of an adverse reaction implies at least a reasonable possibility of a causal relationship between a suspected medicinal product and an AE. An adverse reaction, in contrast to an AE, is characterized by the fact that a causal relationship between a medicinal product and an occurrence is suspected.

Medical judgment should be used to determine the relationship, considering all relevant factors, including pattern of reaction, temporal relationship, de-challenge or re-challenge, confounding factors such as concomitant medication, concomitant diseases and relevant history.

Arguments that may suggest a **reasonable causal relationship** could be:

- The event is consistent **with the known pharmacology** of the drug
- The event is known to be caused by or **attributed to the drug class**
- A **plausible time to onset of the event** relative to the time of drug exposure
- Evidence that the **event is reproducible** when the drug is re-introduced
- **No medically sound alternative etiologies** that could explain the event (e.g. preexisting or concomitant diseases, or co-medications).
- The event is typically **drug-related and infrequent in the general population** not exposed to drugs (e.g. Stevens-Johnson syndrome).
- An indication of dose-response (i.e. greater effect size if the dose is increased, smaller effect size if dose is diminished).

Arguments that may suggest that there is **no reasonable possibility of a causal relationship** could be:

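### Patients treated before consent enter the safety set only if they survive to consent, and their events before signature need not be collected, so the pooled primary incidences are biased downward

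*Protocol*

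**What the plan says.** Section 9.7.1.2 of the Protocol defines the safety set in these terms: "These include those who signed the data release consent form to participate in this study, took Spesolimab IV once at least". It adds a condition on observation after dosing: "and were followed up by the investigator once or more". Seven exclusions, (a) to (g), follow. Exclusion (a) removes "Patients who did not signed (signature missing), or patients who signed on the data release consent form prior to the contract date"; (b) and (c) remove patients infused before the contract or before consent; (e) removes those who fail the inclusion or exclusion criteria.

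The closing paragraph relaxes this for the enumeration period: such cases "will be included in the safety set even if the patients who took Spesolimab IV prior to the contract date or prior to signing" the form. That waives (b) and (c) only. Section 9.2.2.2 also keeps "Patients who have signed the data release consent form" as an inclusion criterion. Section 10.1 allows a legally accepted representative to consent.

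Section 11.2 sets the collection window: events "occurring from the signing date on data release consent form to the end of the study need to be collected".

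Section 9.3.2.1 makes the incidences of AEs, SAEs and AESIs primary outcomes, along with "Adverse events leading to death". Section 9.7.2 runs the safety analysis on the single safety set, with subgroups by demographics and baseline characteristics. The same section later says that the analyses rest on everyone given at least one dose, and section 9.5 commits to "collecting data from all patients who receive Spesolimab IV within a 2-year period" after launch.

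**The concern.** A patient infused first and asked for consent later must be alive when consent is given. For deaths, the interval from infusion to signature is therefore event-free by construction. For non-fatal events the mechanism is different: the patient can still enter, but the window in section 11.2 opens at signature, so an earlier event need not be recorded. Infusion and anaphylactic reactions, which are listed AESIs, are the most exposed because they occur close to dosing.

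Both mechanisms lower the observed incidence among late consenters, and pooling carries that into the primary safety result. The label of complete enumeration adds to the problem, because a reader would take the denominator to be everyone treated when it is everyone treated who later consented.

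**Working it through.** **Reading the rules together**

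1. The closing paragraph of 9.7.1.2 waives (b) and (c). It does not waive (a), nor (e), which enforces the signed-consent criterion of 9.2.2.2.
2. A patient infused before consent therefore enters only once consent is signed. A patient infused before the contract is in the same position: (a) also excludes signatures dated before the contract, so a valid signature must come after the infusion.
3. A representative may sign (10.1), so incapacity does not block entry. No section gives a route for a patient who died before consent.
4. Section 11.2 starts required collection at the signing date. For patients who consent before infusion, this covers all time from dosing. For late consenters it leaves out the time from infusion to signature.
5. Section 9.7.2 states no split by timing of consent.

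**Illustration of size**

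The plan gives no figure to reproduce: section 9.5 sets the target of 21 from prevalence and market conditions. Inputs:

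- N = 21 (section 9.5).
- m = number infused before consent. Not given; assumed 5, 10 or 15.
- p = true risk of the event over follow-up, the same in both groups. Not given; assumed 10%.
- s = share of late consenters' events that fall before signature. Not given; assumed 25%, 50% or 75%.

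Non-fatal event, with the patient kept and pre-signature events unrecorded:

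observed risk = [(21 − m)p + m·p·(1 − s)] / 21

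Fatal event, where late consenters are survivors to signature:

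observed risk = [(21 − m)p + m·p·(1 − s)/(1 − p·s)] / 21

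| m | s | Non-fatal | Fatal |
|---|---|---|---|
| 5 | 25% | (1.6 + 0.375)/21 = 9.4% | (1.6 + 0.375/0.975)/21 = 9.5% |
| 10 | 50% | (1.1 + 0.5)/21 = 7.6% | (1.1 + 0.5/0.95)/21 = 7.7% |
| 15 | 75% | (0.6 + 0.375)/21 = 4.6% | (0.6 + 0.375/0.925)/21 = 4.8% |

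For non-fatal events the relative shortfall is m·s/21 whatever the value of p: 1.25/21 = 6% in the mildest row and 11.25/21 = 54% in the most severe. With p = 5% the non-fatal range is 4.7% to 2.3%; with p = 20% it is 18.8% to 9.3%.

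**The case against.** The strongest reply is that the protocol is less closed than it looks. Several stronger readings are tempting, and the documents do not support them.

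- *Only patients able to sign can enter.* Section 10.1 accepts a representative's consent. The selection is on survival to consent.
- *Severe early events cannot appear.* Section 11.2 sets what must be collected. The abstract counts all reported AEs in dosed patients, and section 9.2.3.1 asks patients to report events noted after starting treatment. Pre-signature events need not be collected, but some may be. The non-fatal figures above assume that none are, so they are the unfavourable end.
- *A missed death gives the size of the pooling bias.* If one treated patient died before consent, 0/21 (exact 95% CI 0 to 16.1%) would be reported where counting that patient gives 1/22 = 4.5% (0.1 to 22.8%). The arithmetic is right, but it measures non-enrolment. That patient is absent whether late consenters are pooled, separated or dropped.
- *Incidence should be read only from patients consented before infusion.* This would set aside patients whom the January 2025 amendment deliberately kept, in a study of 21. That group is not a clean reference either, since it too needs at least one follow-up. Choosing it is a trade-off, and the text does not require it.
- *Late consenters' time at risk should start at consent in a time-to-event analysis.* None is planned; sections 9.3.2.1 and 9.7.2 specify incidences, tests of proportions and logistic regression.

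It is also fair to say that the analyses are exploratory, that the exclusions follow a regulatory guideline not available here, and that an unseen SAP could add a split by timing of consent. The last point weakens any complaint about the missing table taken alone. An SAP could not fully repair the signature rule, the collection window or the all-patients statements, which this protocol fixes.

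**Conclusion.** The concern holds in this form. Late consenters' entry is conditional on survival to consent, their events before signature fall outside required collection, and they are pooled with patients observed from dosing. The effect on the primary safety incidences is downward whenever some events precede signature and go unrecorded. The signature rule also conflicts with the statements in 9.5 and 9.7.2 that all treated patients are covered.

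The size cannot be fixed from the protocol. No launch date, number of late consenters or timing of events is given, so the bias could be trivial or could halve an incidence. The illustration assumes equal true risk in the two groups and that consenting late is unrelated to having had a non-fatal event. The change should be made: safety is the primary objective, and the remedy is cheap.

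**What to change.** 1. **Section 11.2:** for enumeration-period patients infused before consent, start AE, SAE and AESI ascertainment at first infusion, taken retrospectively from the medical record once consent is given.
2. **Section 9.7.2:** show each primary safety outcome for consent on or before first infusion and for consent after it, beside the pooled figure. State that the late-consent group is conditional on survival to consent.
3. **Sections 9.5, 9.7.1.2 and 9.7.2:** report the number treated but not enrolled in the enumeration period, with reasons including death where permitted, and reconcile the all-treated wording with the signature rule.

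Cost: one added table, a count and a few sentences, plus some retrospective abstraction of events. Section 9.2.3.1 already collects the consent and administration dates. No enrolled patient is discarded, and none of this needs a consent waiver beyond whatever is permitted for the count. The strata will be small and their intervals wide, so they serve as description beside the pooled result and not as a comparison.
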